The primary endpoint is to compare the proportion of patients who develop major bleeding (WHO grade 3 or 4) in each arm.

3.3. Secondary Endpoints:

[figure not shown]
Secondary endpoints include:

- The proportion of patients who develop any bleed in each arm
- The total number of units of platelets transfused in each arm during the study period
- Quality of life as measured by EQ-5D-5L in each arm prior to start treatment and at the end of the study
- Safety in each arm

3.4. Description of Treatment:

Patients will be stratified by expected duration of thrombocytopenia (acute versus chronic), and randomized to receive oral EACA at the dose of 1,000 mg twice daily or the infusion of 1 U of single donor apheresis of platelet when untransfused platelet counts are $< 20 \times 10^9/L$ in the out-patient or $< 10 \times 10^9/L$ in the in-patient, as measured on at least twice weekly CBCs (standard of care for cytopenic patients). Schema of the trial is listed in Figure 3.

Study Schema.

3.5. Randomization:

Patients will be randomized on a 1:1 ratio within each strata (acute vs. chronic) to EACA (Arm B) or standard prophylactic platelet transfusions (Arm A) using a standard randomization table. The study is unblinded.

4. Patient Selection:

4.1. Inclusion Criteria:

- Age > 18 with a hematological malignancy
- Informed consent
- Thrombocytopenia with untransfused platelet counts < 20 x 10⁹/L in the out-patient or in the in-patient setting and one of the following criteria:
 1. Acute thrombocytopenia in patients with hematological malignancies who are in remission and are receiving myelosuppressive consolidation chemotherapy that is expected to induce marrow aplasia for at least 2 weeks; or
 2. Acute or chronic thrombocytopenia in patients with acute leukemia (myeloblastic or lymphoblastic) receiving induction or re-induction chemotherapy that is expected to induce marrow aplasia for at least 2 weeks; or Expected chronic thrombocytopenia in patients with newly diagnosed marrow failure syndromes, myelodysplastic syndromes, aplastic anemia, chronic myelomonocytic leukemia or myelofibrosis; or
 3. Expected chronic thrombocytopenia in patients with relapsed or refractory hematological malignancies; or

4. Hematopoietic stem cell transplant recipients with chronic thrombocytopenia due to chronic GVHD or other causes.

4.2 Exclusion Criteria:

- Acute promyelocytic leukemia
- Patient receiving anticoagulation
- Patient receiving antiplatelet agents

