8.5.3 Secondary Endpoint Analysis

One-sided t-test will be used to compare the total number of bleeding episodes noted during the study between the two arms. Two-sided t-test will be employed to compare the total number of units of platelets transfused at the end of the study between the two arms. Appropriate statistical tests (Chi-square test, t-test, Wilcoxon's rank sum test, etc.) will be conducted to compare the each score of the quality of life between the two arms before the study and at the end of the study, respectively. The change of each score of the quality of life from before the study to the end of the study will also be compared between the two arms. The safety in each arm will be also compared with Fisher's exact test. The analyses of secondary endpoints will be performed on the ITT population and the significance level will be kept at 0.05 for all tests.

For the primary and secondary efficacy endpoints, subgroup analyses will be performed by baseline potential prognostic factors. Subgroups will include: age, gender, race, underlying diagnosis, and other disease-related prognostic factors (disease status).

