8.7 Quality of Life Analysis

Quality of life and health outcomes measures are being collected using the EQ-5D-5L instruments before the study and at the end of the study. Means and medians of raw scores of these questionnaires will be summarized for each treatment group for each domain and be compared between the two arms with t-test or Wilcoxon ranks sum test.

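### Each EQ-5D-5L score is tested at baseline, at the end and as change, all unadjusted and with no main comparison; one baseline-adjusted comparison per score would be at least as precise and give one answer

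*Protocol*

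**What the plan says.** Section 3.3 of the protocol lists among the secondary endpoints "Quality of life as measured by EQ-5D-5L in each arm prior to start treatment and at the end of the study". The schedule of events (Table 3, Section 5.1) has the questionnaire on Day 1 and at end of treatment, so a baseline and an end score are planned for each patient who can complete it.

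Section 8.5.3 sets out the comparisons. Tests from an open list (chi-square, t-test, Wilcoxon rank sum and others) will be used "to compare the each score of the quality of life between the two arms before the study and at the end of the study". The next sentence adds: "The change of each score of the quality of life from before the study to the end of the study will also be compared". For the secondary endpoints as a whole, "the significance level will be kept at 0.05 for all tests".

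Section 8.7 covers the same data again: "Means and medians of raw scores of these questionnaires will be summarized for each treatment group for each domain and be compared", by t-test or Wilcoxon rank sum test.

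Every test named in the two sections is an unadjusted two-sample test. Neither section says which comparison answers the secondary objective on quality of life in Section 2.2.

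**The concern.** There are three weaknesses.

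- **The baseline test.** If the questionnaire is completed before the allocation is known, a between-arm baseline difference arises by chance alone. Testing it says nothing about treatment.
- **Two unadjusted tests of the effect.** The end-score test makes no use of the baseline. The change score uses it, but subtracts it in full whatever the real relation between the two measurements. With equal SDs, the change score is noisier than the end score when the correlation is below 0.5 and less noisy above it. Adjustment estimates the slope instead of fixing it at 0 or 1.
- **No main comparison.** Section 6.2 describes five 5-level dimensions and a 100-point visual scale. Counting the visual scale as one score gives 6 scores. Three comparisons each make 6 × 3 = 18 tests, of which 6 × 2 = 12 bear on the treatment effect. When the end-score and change results differ, the protocol does not say which one counts.

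At stake are the precision and the clarity of one secondary endpoint in a trial of 100 patients.

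**Working it through.** **The plan's own figure.** The protocol gives no SD, effect size, correlation or power for quality of life. Its only sample size is for the primary endpoint (Section 8.4: 8% against 30%, one-sided Fisher test at 5%, 45 per arm for 80% power). This reproduces: exact power at 45 per arm is 80.05%, and 45/0.9 = 50 per arm. Only the 50 per arm is used below.

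**Model.** Continuous score, equal SD at both times, linear relation, baseline-to-end correlation r. The documents do not give r, so 0.3 to 0.7 is assumed. Variance of the between-arm contrast, with the end score set to 1:

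- end score: 1
- change: 2(1 − r)
- baseline-adjusted (ANCOVA): 1 − r²

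The reduction from adjustment is r² against the end score. Against change it is 1 − (1 − r²)/(2(1 − r)) = (1 − r)/2.

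| r | End score | Change | ANCOVA | Reduction vs end score | Reduction vs change |
|---|---|---|---|---|---|
| 0.3 | 1 | 1.40 | 0.91 | 9% | 35% |
| 0.5 | 1 | 1.00 | 0.75 | 25% | 25% |
| 0.7 | 1 | 0.60 | 0.51 | 49% | 15% |

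At r = 0.7 the variance that remains is 0.51 of the end-score variance, so the reduction is 1 − 0.51 = 49%.

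**In patients.** ANCOVA matches the end-score test at 50 per arm with 50 × (1 − r²) patients per arm: 46, 38 and 26 for r = 0.3, 0.5 and 0.7, rounded up. It matches the change-score test with 50 × (1 + r)/2: 33, 38 and 43.

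**Illustrative power.** 50 complete pairs per arm, an assumed difference of 0.5 SD, two-sided 0.05 (the protocol does not state sidedness for these tests):

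| r | End score | Change | ANCOVA |
|---|---|---|---|
| 0.3 | 70.5% | 56.1% | 74.6% |
| 0.5 | 70.5% | 70.5% | 82.3% |
| 0.7 | 70.5% | 89.8% | 93.8% |

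**Disagreement between the two planned tests.** The end-score and change statistics correlate √((1 − r)/2), which is 0.59, 0.50 and 0.39. Simulating them as bivariate normal for one score:

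- No true effect: they disagree on significance in 7.5%, 8.2% and 8.7% of trials. At least one is significant in 8.8%, 9.1% and 9.3%.
- True 0.5 SD difference, 50 per arm: they disagree in about 30%, 28% and 28%.

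**The case against.** **The baseline is not ignored.** A reader might infer from the list of unadjusted tests that the baseline data go unused. Section 8.5.3 does not support that: the change score uses the baseline with slope 1. What is lacking is a model that estimates the slope and a comparison named as the main one.

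**Nothing planned is invalid.** A reader might also infer that the planned tests are biased. Under randomisation both the end-score and the change comparison are unbiased on average, each keeps its own 5% error, and chance imbalance is already reflected in the standard error. The 9% chance of at least one significant result arises only if either test may be claimed.

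**The list of tests is open.** It ends with an et cetera, and a statistical analysis plan not shown here could name an adjusted model. That is fair, but every test the protocol does name, in both sections, is unadjusted.

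**The figures are narrow.** They rest on an assumed r and suit the visual scale, not the five 5-level dimensions. End of treatment ranges from platelet recovery to 6 months (Section 5.3), so a high r cannot be presumed. Complete pairs may also fall well short of 50 per arm. In the preliminary cohort 25 of 44 patients (57%) stopped EACA because of death (Table 2), and Section 5.1 limits the questionnaire to patients with a validated translation. All of this stands.

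**The baseline may not precede the allocation.** Table 3, as it can be read, puts randomisation in the screening column and the questionnaire on Day 1. The study is unblinded (Section 3.5), and Section 3.3 promises only a measurement before treatment starts. Section 5.1 places randomisation just before treatment, so the gap may be short, and the table may be damaged in extraction. Still, a baseline answered with knowledge of the arm could carry part of an effect, and adjustment would then distort it. This stands as a condition on the fix.

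**Conclusion.** The point holds as one of precision and clarity. The protocol fixes two unadjusted comparisons of the treatment effect per score, plus an uninformative baseline test, and ranks none of them. For the visual scale, baseline adjustment lowers the variance by 9% to 49% against the end-score test and by 35% to 15% against the change-score test. This assumes r from 0.3 to 0.7, equal SDs, a linear relation and a baseline taken before the allocation is known. The gain is small against the end score when r is low, and small against change when r is high.

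It would be tempting to quote a single gain, such as the equivalent of 33% more patients (1/0.75 = 1.33). That figure belongs to r = 0.5 alone, and nothing in the protocol supports choosing that value. The percentages should not be carried over to the five dimensions. Quality of life is one of four secondary endpoints, and the primary analysis and sample size are unaffected, so the change is worth making but its impact is modest.

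**What to change.** In Sections 8.5.3 and 8.7, replace the three comparisons by one named main comparison per score:

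- **Visual scale:** ANCOVA of the end score on arm, baseline score and the acute/chronic stratum used in the randomisation.
- **Five dimensions:** an ordinal model of the end level on arm and baseline level where the data allow. Collapse sparse levels, or otherwise keep the rank test.
- **Descriptive only:** baseline, raw end and change scores by arm. Drop the between-arm test of baseline.
- **Timing:** state that the baseline questionnaire is completed before the allocation is disclosed, and align Table 3 with this.

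The main cost is wording and slightly more modelling, and no additional questionnaire is needed. With at most about 50 per arm, the ordinal models may meet sparse cells, so the fallback should be written in advance. The change does not solve end scores missing through death or dropout, and one comparison for each of six scores still leaves six tests at 0.05.

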8.6 Safety Analysis

All patients receiving at least 1 dose of study drug will be considered evaluable for safety. Patients will be analyzed for safety according to the treatment which they received. Listings of laboratory test results will

also be generated, and descriptive statistics summarizing the changes in laboratory tests over time will be presented. Exposure to study drug over time will also be summarized. The AE incidence rates, as well as the frequency of occurrence of overall toxicity, categorized by toxicity grades (severity) will be described for each treatment arm and be compared between two arms using two-sided Chi-square test or t-test.

8.7 Quality of Life Analysis

Quality of life and health outcomes measures are being collected using the EQ-5D-5L instruments before the study and at the end of the study. Means and medians of raw scores of these questionnaires will be summarized for each treatment group for each domain and be compared between the two arms with t-test or Wilcoxon ranks sum test.

8.8 Interim Analysis

Three interim analyses are planned after 11 patients in each arm have been randomized and their results have been obtained. Each interim analysis will focus on the primary endpoint, the proportion of patients with major bleeding ever noted during the study. To maintain an overall Type I error rate of 0.05 (1-sided), an O'Brien Fleming approach will be used which requires a 1-sided p-value < 0.001 at the first interim analysis (at 25% of total sample size). If this boundary is not crossed, then the study will continue and the second interim analysis will be conducted at 50% of the total sample size which requires a 1-sided significance level of 0.004. If this boundary is not crossed at the second interim analysis then, the study will continue and a third interim analysis will be conducted at 75% of the total sample size which requires a 1-sided significance level of 0.019. If this boundary is not crossed, the final primary analysis will be performed after completing 100% of the sample size using a 0.043 one-sided significance level.

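### Section 8.8 claims O'Brien-Fleming at one-sided 0.05, but its levels for looks 2 to 4 are the two-sided 0.05 values labelled one-sided; error is not inflated, but looks 2 and 3 are too strict

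*Protocol*

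**What the plan says.** Protocol section 8.8 names the method, the overall error and the side: "To maintain an overall Type I error rate of 0.05 (1-sided), an O'Brien Fleming approach will be used". It then fixes four levels, each labelled one-sided.

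- Look 1: "which requires a 1-sided p-value < 0.001 at the first interim analysis (at 25% of total sample size".
- Look 2: "conducted at 50% of the total sample size which requires a 1-sided significance level of 0.004".
- Look 3: "conducted at 75% of the total sample size which requires a 1-sided significance level of 0.019".
- Final analysis: "using a 0.043 one-sided significance level".

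The timing is introduced by "Three interim analyses are planned after 11 patients in each arm have been randomized". The synopsis repeats the same text. Section 8.5.2 makes the primary test a one-sided Fisher exact test. Section 8.4 assumes major bleeding in 8% (EACA) and 30% (standard of care), with 45 patients per arm raised to 50 for dropout. Section 8.8.1 expects enrolment to be complete before the interim analysis, and patients to stay on their randomised arm if the boundary is crossed.

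**The concern.** Method, number and spacing of looks, overall error and side together determine the levels, so the four figures can be checked. They do not follow from the stated design. The last three are recognisable as the two-sided O'Brien-Fleming values for two-sided 0.05.

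These levels decide when the primary endpoint can be declared positive. A reader who recomputes them will find a boundary that is not the one named, and cannot tell whether the label or the numbers are wrong. In an open-label trial, an interim p-value between 0.004 and 0.0071 could then be argued either way.

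**Working it through.** **Inputs.** Four looks at 25, 50, 75 and 100% and overall one-sided 0.05 (section 8.8); one-sided Fisher test (8.5.2); 8% v 30%, 45 or 50 per arm (8.4).

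**Formula.** Classical O'Brien-Fleming uses z_k = C/√t_k, where t_k is the information fraction. C is solved numerically so that the total crossing probability under the null equals the overall error. The nominal one-sided level is 1 − Φ(z_k), and the nominal two-sided level is twice that.

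**Step 1: reproduce the plan's figures.** Two-sided 0.05 gives C = 2.024 and z = 4.049, 2.863, 2.337, 2.024. The two-sided p-values are 0.00005, 0.0042, 0.0194 and 0.0429. To three decimals these are <0.001, 0.004, 0.019 and 0.043, the plan's figures. Expressed as one-sided p-values, the same boundary is 0.00003, 0.0021, 0.0097 and 0.0215, for an overall one-sided error of 0.025.

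**Step 2: compute the design that is claimed.** One-sided 0.05 gives C = 1.733 and z = 1.733/√0.25 = 3.466, 1.733/√0.50 = 2.451, 1.733/√0.75 = 2.001, and 1.733.

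| Look | Plan | Classical, one-sided 0.05 | Lan-DeMets O'Brien-Fleming type, one-sided 0.05 |
|---|---|---|---|
| 25% | < 0.001 | 0.0003 | 0.0001 |
| 50% | 0.004 | 0.0071 | 0.0055 |
| 75% | 0.019 | 0.0227 | 0.0219 |
| 100% | 0.043 | 0.0415 | 0.0427 |

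Looks 2 and 3 are below both versions. The final level is above the classical value but rounds to the Lan-DeMets one. Look 1, read as an operating threshold, is above both.

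**Step 3: overall error.** Used literally as one-sided levels, the plan's figures spend cumulatively 0.0010, 0.0047, 0.0207 and 0.0489 by normal theory. With 0.00005 at look 1 the total is 0.0485. Exact enumeration of the sequential Fisher test at a common rate of 19% (the mean of 8% and 30%) gives about 0.027 at 12/25/37/50 per arm and 0.026 at 11/22/34/45. The largest value over common rates from 5% to 95% is about 0.033.

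**Step 4: power and early crossing under 8% v 30%, by exact enumeration.**

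| Quantity | Per-arm looks | Plan | Classical one-sided |
|---|---|---|---|
| Crossed by look 2 | 12/25 | 12.9% | 20.6% |
| Crossed by look 2 | 11/22 | 9.2% | 15.1% |
| Crossed by look 3 | 12/25/37 | 55.5% | 56.1% |
| Crossed by look 3 | 11/22/34 | 49.7% | 55.2% |
| Overall power | 12/25/37/50 | 0.831 | 0.831 |
| Overall power | 11/22/34/45 | 0.782 | 0.782 |

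**Step 5: results that would be judged differently.** At look 2 with 25 per arm, 0 v 7, 1 v 9, 2 v 11 and 3 v 12 major bleeds have one-sided Fisher p of 0.0048, 0.0053, 0.0041 and 0.0061. All meet 0.0071 and fail 0.004. At look 1 with 11 per arm, 0 v 8 (0.0005) and 1 v 9 (0.00095) meet 0.001 and fail 0.0003, but with 11 per arm the chance of crossing at look 1 is only 0.2%.

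**The case against.** The strongest reply is that section 8.8 promises control of the overall one-sided error at 0.05, and the stated levels deliver it. Power is the same with either set. Section 8.8.1 expects all patients to be enrolled before the interim analysis and treatment to continue after a crossing, so an early crossing would save no patients and change nobody's assigned treatment. All of this stands. It limits the consequence but does not make the levels those of the named design.

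Some stronger readings are tempting, and the protocol does not support them.

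- **That the false-positive rate is inflated.** It is not: 0.0489 by normal theory, and less with Fisher's test. A figure just above 0.05 (0.0508) arises only if the looks fall at 22, 44, 66 and 100%, a schedule that appears nowhere in the plan.
- **That all four levels are the two-sided values.** Only looks 2 to 4 match. The first matches only if it is the three-decimal display of 0.00005; as a threshold it belongs to neither set.
- **That the final level is plainly too loose.** The protocol says only that an O'Brien-Fleming approach is used, and 0.043 agrees with the Lan-DeMets form.
- **That 11 per arm contradicts 25%.** It is 22/100 = 22% of those randomised but 11/45 = 24.4% of the evaluable target. The base is unstated; the count is not wrong.
- **That the trial is really a two-sided 0.05 design.** Sections 8.4, 8.5.2 and 8.8 all say one-sided for the primary comparison. A single final Fisher test at 0.0215 would have power of only 0.68 at 45 per arm and 0.74 at 50, which does not fit the 80% in section 8.4.

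**Conclusion.** The point holds as a mislabelled boundary. The levels at looks 2 to 4 are two-sided 0.05 O'Brien-Fleming p-values presented as one-sided levels for one-sided 0.05. Looks 2 and 3 are clearly too strict for the stated design (0.004 against 0.0055 to 0.0071; 0.019 against 0.0219 to 0.0227). The final level differs only from the classical value, and look 1 is too loose only if taken literally. Error control and overall power are intact. What changes is when the boundary is crossed, chiefly at look 2, and section 8.8.1 limits what follows from that.

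The figures assume equally spaced looks, independent patients with complete outcomes at each look, and the event rates of section 8.4. It should be corrected because these are prespecified thresholds for the primary endpoint and the correction is cheap.

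**What to change.** In section 8.8 and the synopsis, do one of the following.

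1. Replace the four levels by the classical one-sided 0.05 values: 0.0003, 0.0071, 0.0227 and 0.0415.
2. Name Lan-DeMets O'Brien-Fleming-type spending at one-sided 0.05, and compute each level from the actual number of patients at that look (0.0001, 0.0055, 0.0219 and 0.0427 if the looks are equally spaced).

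In either case, state whether the look fractions are of 90 evaluable or 100 randomised patients, and give the number per look on that base.

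The cost is wording in two places and no extra patients. The first option makes the final level slightly less favourable, 0.0415 instead of 0.043. At 50 per arm no possible table has a Fisher p between the two, so no final decision would change; at 45 per arm four tables do (for example 7 v 15, p = 0.0423).

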All patients receiving at least 1 dose of study drug will be considered evaluable for safety. Patients will be analyzed for safety according to the treatment which they received. Listings of laboratory test results will also be generated, and descriptive statistics summarizing the changes in laboratory tests over time will be presented. Exposure to study drug over time will also be summarized. The AE incidence rates, as well as the frequency of occurrence of overall toxicity, categorized by toxicity grades (severity) will be described for each treatment arm and be compared between two arms using two-sided Chi-square test or t-test.

Quality of Life Analysis

Quality of life and health outcomes measures are being collected using EQ-5D-5L instruments before the study and at the end of the study. Means and medians of raw scores of these questionnaires will be summarized for each treatment group for each domain and be compared between the two arms with t-test or Wilcoxon ranks sum test.

Interim Analysis

Three interim analyses are planned after 11 patients in each arm have been randomized and their results have been obtained. Each interim analysis will focus on the primary endpoint, the proportion of patients with major bleeding ever noted during the study. To maintain an overall Type I error rate of 0.05 (1-sided), an O'Brien Fleming approach will be used which requires a 1-sided p-value < 0.001 at the first interim analysis (at 25% of total sample size). If this boundary is not crossed, then the study will continue and the second interim analysis will be conducted at 50% of the total sample size which requires a 1-sided significance level of 0.004. If this boundary is not crossed at the second interim analysis then, the study will continue and a third interim analysis will be conducted at 75% of the total sample size which requires a 1-sided significance level of 0.019. If this boundary is not crossed, the final primary analysis will be performed after completing 100% of the sample size using a 0.043 one-sided significance level.

TABLE OF CONTENTS

Protocol Synopsis

- 1. Background**
 - 1.1 Thrombocytopenia in Patients With Hematological Malignancies**
 - 1.2 Fibrinolysis and Inhibition of Fibrinolysis with Epsilon Aminocaproic Acid**
 - 1.3 Preliminary studies**
 - 1.4 Rationale for the study**
 - 2. Study Objectives and Hypothesis**
 - 2.1 Primary Objective**
 - 2.2 Secondary Objective**
 - 2.3 Hypothesis**
 - 3. Investigational Plan:**

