8.2 Analysis Population

Intention to treat (ITT) population: The ITT population includes all patients who are randomized to the study. Patients will be analyzed according to the treatment to which they were assigned.

Safety Population: The safety population includes all patients who have received at least 1 dose of EACA. Patients included in the safety population will be analyzed according to the treatment they received.

Per-protocol Population: The per-protocol population includes all patients who are randomized, receive at least one dose of study drug, and have no major protocol violations that could be expected to impact response data, such as: failure to satisfy one or more eligibility criteria, administration of other anti-cancer therapy concurrent with study drug, and administration of incorrect study drug doses. Major protocol violations will be finalized and documented prior to final data analysis.

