8.4 Determination of Sample Size

This randomized, open-label phase II study is designed to compare proportion of patient with bleedings noted during the study. Patients will be assigned to receive prophylactic EACA (experimental arm) or prophylactic platelet (standard of care) in a 1:1 fashion. Previous studies suggest that the proportions of patients with major bleeding will be expected to be 8% and 30% in experimental arm and standard of care arm, respectively. With one sided Fisher's exact test, the sample size of 45 patients in each arm will achieve a power of 80% at the significance level of 5% to test whether prophylactic EACA can prevent major bleeding better than the standard of care. After adjusting for a 10% drop out rate, the actual required sample size will be 50 patients per arm. Therefore, the total sample size of the study will be 100 patients.

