8.5.2 Primary Endpoint Analysis

The primary analysis of the primary endpoint will be performed using a one-sided fisher exact test to compare the proportions of patients with major bleeding during the whole study between the two arms. The significance level is set at 0.05. This primary analysis will be based on the ITT population.

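### The final primary test has two significance levels (0.05 and 0.043), the stated 80% power ignores the three interim looks, and 8.8.1 does not match the look schedule in 8.8

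*Protocol*

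**What the plan says.** **Level of the primary test.** Section 8.5.2 specifies a one-sided Fisher exact test of the proportions with major bleeding and adds: "The significance level is set at 0.05. This primary analysis will be based on the ITT population". The synopsis efficacy text says the same. Section 8.8 sets out an O'Brien-Fleming plan: "To maintain an overall Type I error rate of 0.05 (1-sided"), the looks use one-sided levels of 0.001, 0.004 and 0.019 at 25%, 50% and 75% of the sample, and then "the final primary analysis will be performed after completing 100% of the sample size using a 0.043 one-sided significance level". The synopsis interim text repeats this, again "using a 0.043 one-sided significance level".

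**Power.** Section 8.4 assumes major bleeding in 8% (EACA) and 30% (platelets) and states that "the sample size of 45 patients in each arm will achieve a power of 80% at the significance level of 5" per cent. It continues: "After adjusting for a 10% drop out rate, the actual required sample size will be 50 patients per arm". It does not mention interim looks. Section 8.2 defines the population for the primary analysis: "The ITT population includes all patients who are randomized to the study".

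**Looks.** Section 8.8 says "Three interim analyses are planned after 11 patients in each arm have been randomized" and have results. Section 8.8.1 refers to the interim analysis in the singular, expects enrolment to be complete before it, and expects patients to stay on their randomised arm if the boundary is crossed. Section 5.3 gives 14 months for accrual, up to 1 year of treatment and follow-up for the last patient, and end of treatment at 6 months for patients whose platelets do not recover.

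**The concern.** The sections that fix the decision rule, the power and the interim conduct do not describe one design.

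- **Threshold.** A reader who follows 8.5.2 tests at 0.05, and one who follows 8.8 tests at 0.043. In an open-label trial the pass mark should not be open to choice once the p-value is known.
- **Power.** The stated figure belongs to a fixed design with a single test, which is not the plan in 8.8.
- **Conduct.** If the early looks happen while patients are still being enrolled, a boundary crossing raises the question of whether enrolment goes on. The protocol says only that patients are expected to continue on their arm.

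**Working it through.** **Inputs.** Event rates 8% and 30%, one-sided Fisher test, 45 evaluable or 50 randomised per arm (8.4, 8.5.2). Levels 0.001, 0.004, 0.019 and 0.043 at 25%, 50%, 75% and 100% (8.8). Looks are taken at 11/22/34/45 per arm, or 12/25/37/50 if all 50 count. Accrual is 14 months (5.3).

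**1. The plan's own figure.** Power is the sum, over all tables (x, y) with Fisher p ≤ α, of Bin(x; n, 0.08) × Bin(y; n, 0.30). With n = 45 and α = 0.05 this gives 0.8005, so the stated 80% reproduces for one test. With n = 50 it gives 0.8455.

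**2. Power under 8.8.** The same enumeration is run stage by stage, removing tables that have already crossed.

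| Per arm | Look 1 | Look 2 | Look 3 | Final at 0.043 | Total | Total if final at 0.05 |
|---|---|---|---|---|---|---|
| 11/22/34/45 | 0.0019 | 0.0904 | 0.4048 | 0.2845 | 0.7817 | 0.8052 |
| 12/25/37/50 | 0.0036 | 0.1252 | 0.4266 | 0.2753 | 0.8306 | 0.8498 |

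The looks cost 0.8005 − 0.7817 = 0.019 at 45 per arm, and 0.8455 − 0.8306 = 0.015 at 50.

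**3. How often the two levels disagree.** The chance of reaching the final test with p between 0.043 and 0.05 is the difference between the last two columns: 0.8052 − 0.7817 = 0.0235 at 45 per arm and 0.8498 − 0.8306 = 0.0192 at 50. If the control rate were 20% (an assumption), it would be 0.0429 and 0.0410. The tables concerned, EACA versus control, with at most 25 control events:

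- 50 per arm: 2 v 8 (p = 0.0458), 4 v 11 (0.0453), 7 v 15 (0.0448), 12 v 21 (0.0441), 13 v 22 (0.0464), 14 v 23 (0.0485).
- 45 per arm: 2 v 8 (0.0448), 4 v 11 (0.0437), 8 v 16 (0.0470), 15 v 24 (0.0441), 16 v 25 (0.0449).

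**4. Type I error.** In normal theory the listed levels give 0.0489 overall; replacing the final 0.043 with 0.05 gives 0.0551. The Fisher test is conservative, however. Over common event rates from 5% to 50% the exact maximum is 0.0321 (45 per arm) or 0.0328 (50) with a final 0.043, and 0.0387 or 0.0362 with a final 0.05.

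**5. Timing of the looks.** Assume even accrual, 100/14 = 7.14 patients per month. Look 1 needs 22–25 patients, enrolled by 3.1–3.5 months; look 2 needs 44–50, enrolled by 6.2–7.0 months. Allow 6 months to outcome:

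- Look 1 falls at 9.1–9.5 months, with 65–68 of 100 enrolled.
- Look 2 falls at 12.2–13.0 months, with 87–93 enrolled.
- Look 3 falls after enrolment is complete.

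For look 1 to follow full enrolment, results would have to take at least 14 − 3.5 = 10.5 to 14 − 3.1 = 10.9 months. For look 2 the figure is 14 − 7.0 = 7.0 to 14 − 6.2 = 7.8 months. If the 1-year outer limit in 5.3 is taken as time to results, look 1 falls at 15.1–15.5 months and all looks follow enrolment.

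**6. Chance of a crossing at look 1 or 2 at the design rates.** 0.0019 + 0.0904 = 0.092, or 0.0036 + 0.1252 = 0.129.

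**The case against.** - **The two levels can be read together.** Section 8.8 names 0.05 as the overall error and derives 0.043 for the final test, so 8.5.2 could be taken as giving the overall level. That is a sensible reading, but 8.5.2 and the synopsis efficacy text attach 0.05 directly to the test, do not call it overall and do not refer to 8.8. The contradiction stands, with small stakes.
- **The power sentence in 8.4 is true as written, and 50 per arm exceeds 80% even with the looks.** Both are correct. The loss is about 2 points and no sample size change follows. What stands is that the figure does not belong to the plan that will be run.
- **Section 8.8 implies that a crossing ends the sequence, since continuation depends on not crossing.** This is fair as an inference, but the effect on enrolment is still unstated.
- **The timing depends on assumptions.** It does: even accrual and 6 months to outcome. Look 1 contributes only 0.2–0.4 points of the crossing probability, and at look 2 only about 7–13 patients would remain to be enrolled. The mismatch between three looks and one does not depend on timing.
- **Section 2.3 calls this a non-inferiority trial, which could make restated power figures obsolete.** That is a separate matter. The figures here are for the superiority test that 8.4 and 8.5.2 specify.

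**Conclusion.** The point holds and should be fixed. The threshold is the main part: the same final test has two levels, and they give opposite conclusions in about 2% of trials at the design rates (about 4% with an assumed 20% control rate). False positives are not inflated beyond 0.05 under either reading.

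The power part is an inaccurate description with a small effect: 78.2% and not 80% at 45 per arm, and 83.1% if all 50 per arm contribute an outcome to the ITT analysis.

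The number of looks is inconsistent between 8.8 and 8.8.1 whatever the timing. That looks 1 and 2 precede the end of enrolment is conditional on the accrual and outcome-time assumptions. If they do, there is a 9–13% chance at the design rates of a crossing whose consequence for enrolment is not stated.

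**What to change.** 1. In 8.5.2 and the synopsis efficacy text, give 0.05 one-sided as the overall level and 0.043 as the nominal level of the final test, with a reference to 8.8.
2. In 8.4 and the synopsis, state power with the looks: about 78% at 45 evaluable per arm, and 83% if all 50 per arm are analysed as ITT.
3. Reconcile 8.8.1 with 8.8 and 5.3: three looks, when each is expected relative to enrolment, and what crossing a boundary changes.

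The cost is wording only, with the sample kept at 100. The stated power at 45 evaluable per arm drops to just under 80%. Restoring 80% there would take 47 evaluable per arm (four-look power 0.8004); 47/0.9 = 52.2, so 53 per arm or 106 in total. That is given for information and is not proposed.
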